9.3 Variables

Demographics

Basic demographics including patient initials, age (year and month of birth), sex, weight, height, name of institution, department and physician will be taken and recorded.

Diagnosis and Medical History

Diagnosis and medical history including previous TB history or vaccination, will be taken and recorded and will include the following items to get patient's medical status:

- CD related history ; date of pediatric CD diagnosis, involved intestinal area, presence of draining fistula, previous CD related therapy including antibiotics, steroids, 5-ASA, Immunosuppressants, biologics and nutritional therapy
- Previous TB history ; presence of TB, TB treatment regimen received, completeness and appropriateness of the therapy regimen, vaccination
- Other medical history ; history of previous disease(s), concurrent disease(s), history of allergy, pregnancy etc.

PPD Skin Test

PPD skin test will be performed and recorded. It will include: Date of PPD test, induration at PPD test site (in mm). (Refer to MFDS Guideline for Latent TB Management in TNF-Antagonist Use and TB screening Aide provided by AbbVie.)

Chest X-ray

Chest X-ray interpretation result will be taken and recorded and will include: Date of Chest-X-Ray, presence of latent or active TB lesion. (Refer to MFDS Guideline for Latent TB Management in TNF-Antagonist Use and TB screening Aide provided by AbbVie.)

Interferon gamma release assay

Interferon gamma release assay will be performed, recorded and will include: date of interferon gamma release assay and result. (Refer to MFDS Guideline for Latent TB Management in TNF-Antagonist Use and TB screening Aide provided by AbbVie.)

Treatment with Humira®

Patients will be administered Humira® as per the package label. Unit dose, frequency, length of treatment (start date, end date) will be recorded on the appropriate case report form.

Concomitant Medication

Concomitant medications, including TB prophylaxis regimen, corticosteroids, immunosuppressants, will be recorded and will include: generic name (brand name in case of combination drug), total daily dose, length of administration (start date and end date), indication(s).

Safety (Adverse Event)

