Regardless of results of causality assessment, presence of adverse event(s), type of adverse event(s), onset, end date, severity, causality assessment by physician on the adverse event(s), action taken, outcome will be captured, during the study, from the first administration to the surveillance period (from informed consent to up to 70 days following the last administration of Humira®) (Section 11.0 Management and Reporting of Complaints).

Effectiveness

From the patients treated with Humira®, the effectiveness data (i.e. PCDAI score) at previous times before Humira® treatment, at 4 weeks (visit window: ± 1 week) and at 6 months (visit window: ± 4 weeks) post-treatment will be collected. (CDAI score will be collected as well, if possible.)

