† The mean number of patients: The number of patients prescribed with anti-TNF agents for relevant disease codes (K500, K501, K508 or K509); source: Health Insurance Review & Assessment Service; unit: people

‡ Percent: calculated by dividing the mean number of patients by the number of patients diagnosed

3) Difficulties in getting patients' consents

Pediatric CD is indicated for pediatric patients, it is difficult to get pediatric patients' consents from their parents.

However, we will make every effort to enroll maximum number of subjects. We expect maximum 141 patients will be recruited [Table 2].

[Table 2] The number of subjects expected to be enrolled in this study

Classification	No. of subjects
Enrolled subjects as of October, 2016	100
- subject who start Humira treatment after enroll in the study	71
- subject who starts Humira treatment before enroll in the study	29
Estimated No. of subjects to be enrolled	Approx. 41
- subject who will start Humira treatment after enroll in the study	31*
- subject who starts Humira treatment before enroll in the study	10
Total	Approx. 141

* Calculated as follows: 5.07 (mean number of newly diagnosed patients per month) x 6 months (remaining enrollment period) = 30.42

About 15 investigators across the country will be participating in this surveillance and the number of subjects to be collected by each investigator will vary.

Study Duration

The study duration designated by MFDS is from 12 September 2013 to 11 September 2017. The study will start after the launch of the product as a new drug for pediatric CD and the final report will be submitted to MFDS by 11 Dec 2017. Interim study reports will be submitted to MFDS every 6 months for the first 2 years, then annually thereafter during PMS period.

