9.7 Data Analysis

Justification for the planned sample size

Information on at least 600 subjects will be collected in this surveillance study in accordance with the Korean regulations on New Drug Re-examination (i.e. New Drug Re-examination Standards: Ministry of Food and Safety (MFDS)).

The sample size of 600 has been selected in order to give at least 95% probability of detecting at least one uncommon SAE that occurs in the Korean patient population at a rate of at least 0.5%. This estimate is based on the assumption that the occurrence of AEs has a Poisson distribution and that if the population rate of occurrence of an AE is 0.5% then the expected number of AEs in the proposed sample size of 600 would be 3. The probability of observing 1 or more events with a Poisson parameter of 3 is 0.95 or 95%.

If we have an AE with a population probability of 0.5% then the expected number of events in a sample size of 600 will be 3. Using the Poisson Distribution with a parameter of 3 the probability of getting zero AEs in our sample size of 600 is given by the formula:

$$\Pr\{X = 0\} = \frac{3^0 \times e^{-3}}{0!} = 1 \times 0.0498 = 0.0498$$

The probability, therefore, of having 1 or more AEs in that sample size is $1 - 0.0498 = 0.9502$.

At least 600 subjects were to be collected for surveillance to meet the local regulatory requirements, but number of subjects to be enrolled was adjusted to 141 subjects. (Refer to section 9.5)

Analysis Population

Number of collected and analyzed patient will be presented as following items: Contracted cases, collected number of CRFs, safety-evaluable cases, effectiveness-evaluable cases, number of drop-out cases, Reasons for drop-out

The safety analysis data set will include all subjects who have received at least one administration of Humira® following the initiation of surveillance and have completed follow up for the safety information.

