For induction effectiveness of Humira®, the effectiveness analysis data set will include all subjects who have been administered Humira® and prescribed Humira® for 4 weeks including induction period (± 1 week) and for whom effectiveness evaluation parameters have been recorded. And for maintenance effectiveness of Humira®, effectiveness analysis data set will include all subjects who have been administered Humira® and prescribed Humira® for 6 months (± 4 weeks) and for whom effectiveness evaluation parameters have been recorded. The subjects whose effectiveness evaluation was not properly conducted because their data from evaluation parameters were missing or they discontinued administration prior to the effectiveness evaluation will be excluded from the evaluation.

Safety Analysis

The adverse events will be coded by MedDRA dictionary. The number and percentage of subjects reporting any serious adverse events/adverse drug reactions will be tabulated overall and by MedDRA 17.0 or more recent version, in preferred term. The number and percentage of subjects reporting unexpected (unlabeled) adverse drug reactions will be tabulated in a similar fashion.

To investigate the factors affecting the safety, the number and percentage of subjects reporting adverse events will also be classified by various background factors (e.g., demographic factors, treatment factors such as medical history, dosing and administration, concomitant medications, beginning of administration before/after the registration date, etc.) and tabulated. If the incidence of adverse events in the subjects who began the administration before/after the registration date has statistical significance, it will be presented as a separate item. In addition, if there are patients who have already been

administered Humira® when participating in the surveillance, their adverse events from the first administration of Humira® to the inclusion will be presented in a separate table. If data from special patient groups are collected, they will be extracted and tabulated separately for adverse events/adverse drug reactions.

Effectiveness Analysis

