The effectiveness assessment of Humira® induction therapy and maintenance therapy will be presented by the number and percentage of the subjects with clinical response. Clinical response is defined as decrease in PCDAI score from baseline by ≥ 15 points and if CDAI score is collected, Clinical response is defined as decrease in CDAI score from baseline by ≥ 70 points.

To investigate the factors affecting the effectiveness, the number and percentage of subjects with clinical response will also be classified by background factors (e.g., demographic factors, treatment factors such as medical history, dosing and administration, concomitant medications, beginning of administration before/after the registration date, etc.) and tabulated. If the effectiveness evaluation of above factors has statistical significance, it will be presented as a separate item.

Statistical Methods

The descriptive statistics for safety and effectiveness parameter in each year will be presented in annual reports.

In final report (Re-examination report), safety and effectiveness outcome by background factor will be summarized and analyzed. The analysis for categorical variables will be performed using chi-square test or fisher's exact test and continuous variables will be performed using Wilcoxon rank sum test or t-test. Also, incidence rate of adverse event collected in overall PMS period will be analyzed and 95% CI will be presented.

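### The only adverse event incidence with a planned 95% CI pools about 39 of 141 subjects already on Humira at enrolment with about 102 followed from first dose, and no CI is planned for the latter alone

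*Combined protocol and SAP*

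**What the plan says.** Under Statistical Methods, section 9.7 plans one interval estimate: the "incidence rate of adverse event collected in overall PMS period will be analyzed and 95% CI will be presented". No CI is planned for any subgroup.

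The safety set in section 9.7 takes "all subjects who have received at least one administration of Humira® following the initiation of surveillance", provided safety follow-up is complete. It does not exclude subjects already on treatment at enrolment. Table 2 in section 9.5 counts these on their own line ("subject who starts Humira treatment before enroll in the study"): 29 of the 100 enrolled by October 2016, and 10 of about 41 still expected.

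The plan treats the two groups differently in three places, all in the Safety Analysis part of section 9.7:

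- For subjects already on Humira at entry, "their adverse events from the first administration of Humira® to the inclusion will be presented in a separate table".
- Without any condition, "the number and percentage of subjects reporting adverse events will also be classified by various background factors", and start before or after registration is one of those factors.
- If the incidence in "subjects who began the administration before/after the registration date has statistical significance, it will be presented as a separate item".

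On timing, section 9.2 sets six months of observation counted from the first dose. Section 9.3 captures adverse events "from the first administration to the surveillance period (from informed consent to up to 70 days following the last administration of Humira". Section 11.1.4 starts SAE reporting at the patient's authorization or consent.

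Section 7.0 plans to compare the safety data with the label. Section 8.0 hypothesises a safety profile consistent with phase 3.

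**The concern.** A new starter is observed from the first dose. A prior starter's six months also run from the first dose, but that dose came before inclusion. If events before inclusion are kept apart, the observed part of that window is shorter, and it is empty for anyone more than six months on drug at registration. If those events are counted, data collected in retrospect enter the estimate. Either way the two groups do not contribute the same quantity, and the pooled percentage is not the incidence over six months from first dose.

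A reader who sets the surveillance result beside the label or phase 3 will naturally use the figure that carries an interval. As planned, that figure is the mixed one. The new-starter percentage will be in a table, but without an interval, and it is given prominence only if a test with unequal and small groups reaches significance. A non-significant result in that test would not show that pooling is harmless.

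**Working it through.** **Inputs from section 9.5, Table 2.** The plan's total reproduces: 71 + 29 = 100 enrolled; 31 + 10 = 41 expected (the 31 is 5.07 × 6 = 30.42, rounded up); 100 + 41 = 141.

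**Split.**
- New starters: 71 + 31 = 102, and 102/141 = 72.3%.
- Prior starters: 29 + 10 = 39, and 39/141 = 27.7%.

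These are projections, given as approximate in the plan, but 29 of the 39 were already enrolled.

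**Assumptions.** The documents give no adverse event rate, no time on drug at entry, and no alpha for the background-factor tests. Every rate below is assumed, and the tests are taken as two-sided at 0.05.

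**Power of the test that triggers a separate item.** With 102 against 39 subjects, I summed the binomial probabilities of all tables that reject:

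| Assumed rates, new vs prior | Fisher | Chi-square, uncorrected |
|---|---|---|
| 30% vs 15% | 41% | 45% |
| 50% vs 25% | 75% | 79% |

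At 30% against 15%, a twofold difference would more often than not fail to trigger the separate item.

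**How far pooling can move the figure.** Take a constant hazard, a new-starter incidence p = 20%, and a counted window for prior starters that is r times as long. Then prior = 1 − (1 − p)^r, and pooled = (102p + 39 × prior)/141.
- r = 1: pooled = 20.0%.
- r = 0.5: prior = 1 − 0.8^0.5 = 10.6%, and pooled = (20.4 + 4.1)/141 = 17.4%.

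Under section 9.2, r would not exceed 1 if events before inclusion are left out. A longer window would need follow-up beyond six months from first dose, for example through the 70-day wording in section 9.3. The model ignores selection of patients who tolerate the drug and any change of hazard over time, so it illustrates sensitivity and is not a bias estimate.

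**Effect of the counting rule.** Each prior starter whose only event came before inclusion moves the pooled incidence by 1/141 = 0.71 points. With 20% in each of two equal, independent windows (before and after inclusion), such subjects number 39 × 0.2 × 0.8 = 6.2, or 6.2/141 = 4.4 points.

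**Precision if the groups are reported separately.** Half-width = 1.96 × √(0.2 × 0.8/n), at an assumed 20%; upper limit at zero events = 1 − 0.025^(1/n), the exact two-sided 95% limit.

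| Group | n | Half-width, points | Upper limit at zero events |
|---|---|---|---|
| New starters | 102 | 7.8 | 3.6% |
| Prior starters | 39 | 12.6 | 9.0% |
| Pooled | 141 | 6.6 | 2.6% |

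The new-starter interval is wider than the pooled one by √(141/102) = 1.18.

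**Rare events.** Section 9.7's Poisson method reproduces its own figure: 1 − e^(−3) = 0.9502 for 600 subjects and a 0.5% rate. By the same method the chance of at least one such event is 1 − e^(−0.51) = 40% with 102 subjects and 1 − e^(−0.705) = 51% with 141. This is a reason to keep the pooled figure as well.

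**The case against.** The strongest reply is that section 9.7 already separates the groups. Number and percentage by start before or after registration are tabulated without condition, so the test suppresses no data, and any reader can compute an interval from the counts. Sections 7.0 and 8.0 set no margin or test and do not name the pooled CI as the tool for the label comparison. All of that stands, and it keeps the point modest. What it leaves is that the plan chose to give an interval to one figure, and that figure is not the one best suited to the comparison.

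A reader might infer that the numerator is simply undefined. That is too strong. The separate table, and the parenthesis in section 9.3 that starts the surveillance period at consent, make exclusion of events before inclusion the likelier reading. The reference to the overall PMS period most naturally means cumulative as against annual reporting. The opening words of the section 9.3 phrase still point to first administration, and no sentence states the rule, so this part needs only a clarification.

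A reader might also infer that prior starters are a proven survivor group who bias the rate downwards. The documents do not establish this. Section 9.2 speaks of patients receiving Humira during the study period, and the safety set requires a dose after surveillance begins, not after the subject's own registration. Selection is plausible, but its size and direction are unknown. Section 9.9 already discloses reporting bias with historical data.

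**Conclusion.** The point holds and should be fixed, with medium confidence. About 28% of the subjects behind the plan's only interval estimate do not share the observation window of the rest, and the group followed from first dose gets no interval of its own. The 39/102 split follows from Table 2. The power of 41 to 45% and the illustrated shift from 20.0% to 17.4% rest on assumed rates and windows. The documents do not show that the pooled incidence is biased in a given direction or by a given amount. They show only that it estimates something other than incidence from first dose.

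**What to change.** In section 9.7, drop the significance condition on the before/after split and report the incidence of adverse events, adverse drug reactions and SAEs, with exact 95% CIs, for:

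- (a) subjects first dosed after registration, as the basis for comparison with the label and phase 3;
- (b) subjects first dosed before registration;
- (c) all subjects pooled, kept for rare SAEs.

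State that events before registration in group (b) appear in the separate table already planned and do not enter the incidence in (b) or (c). State also that SAEs and unexpected adverse drug reactions from that period are listed there, so that none is lost. For group (b), report time on drug at registration and length of follow-up after it.

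Reconcile the wording on observation and on the start of event collection in sections 9.2, 9.3 and 11.1.4. Section 9.2 must be included: its clock from first dose conflicts with counting group (b) from registration.

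The cost is small. No new data are needed, because "length of treatment (start date, end date) will be recorded on the appropriate case report form" and section 9.7 already uses the registration date. The price is precision: at an assumed 20%, a half-width of 7.8 points for (a) against 6.6 pooled, and 12.6 points for (b), which can be read only as a rough figure.

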9.8 Quality Control

Prior to the initiation of the study, an investigator's meeting or initiation visit will be held with AbbVie personnel or his/her designee, the investigators and their study coordinators. This meeting will include a review of the protocol and CRF completion.

Investigator must assure that the study is conducted in accordance with the protocol and all relevant regulations and CRF is completed accurately.

CRF will be reviewed by CRAs at AbbVie or their designees for completeness and conclusiveness and when necessary, query will be generated and will be resolved by the site staffs.

All data hand-entered in the database will be verified by a double-key entry procedure. Any discrepancies will be reviewed against the hard copy CRF and corrected. After completion of the entry process, computer logic checks will be run. Any necessary corrections will be made to the database and documented.

9.9 Limitations of the Research Methods

Open-label data from non-randomized patients; reporting bias with historical safety data.

9.10 Other Aspects

NA

10.0 Protection of Human Subjects

Patient written authorization form to use and/or disclose personal and/or health data from legal patient or representative must be obtained prior to enrolling the patient and the physician is required to document this authorization.

However, informed consent will not be required because as local pharmaceutical law does not require informed consent for regulatory-required post-marketing surveillance.

Patient confidentiality must be maintained at all times; therefore demographics that could identify the patients will not be collected.

Monitoring for any sites is not required. However internal consistency check for completeness and consistency of data will be done to ensure integrity of the information reported.

11.0 Management and Reporting of Complaints

A Complaint is any written, electronic, or oral communication that alleges deficiencies related to the physical characteristics, identity, quality, purity, potency, durability, reliability, safety, effectiveness, or performance of a product/device after it is released for distribution.

The investigational product in this trial contains both:

- Biologic compound(s) and
- Device component(s) (pre-filled syringe, pen).

Complaints associated with any component of this investigational product must be reported to the Sponsor (Section 11.2.2). For adverse events, please refer to Sections 11.1.1 through 11.1.6. For product complaints, please refer to Section 11.2.

11.1 Medical Complaints

11.1.1 Adverse Event Definition and Serious Adverse Event Categories

An adverse event (AE) is defined as any untoward medical occurrence in a patient, which does not necessarily have a causal relationship with their treatment. An adverse event can therefore be any unfavorable and unintended sign (including an abnormal laboratory finding), symptom, or disease temporally associated with the use of a medicinal product, whether or not the event is considered causally related to the use of the product.

Such an event can result from use of the drug as stipulated in the labeling, as well as from accidental or intentional overdose, drug abuse, or drug withdrawal. Any worsening of a pre-existing condition or illness is considered an adverse event.

If an adverse event meets any of the following criteria, it is considered a serious adverse event (SAE):

Death of Patient:	An event that results in the death of a patient.
Life-Threatening:	An event that, in the opinion of the investigator, would have resulted in immediate fatality if medical intervention had not been taken. This does not include an event that would have been fatal if it had occurred in a more severe form.□
Hospitalization:	An event that results in an admission to the hospital for any length of time. This does not include an emergency room visit or admission to an outpatient facility.
Prolongation of Hospitalization:	An event that occurs while the study patient is hospitalized and prolongs the patient's hospital stay.
Congenital Anomaly:	An anomaly detected at or after birth, or any anomaly that results in fetal loss.
Persistent or Significant Disability/Incapacity:	An event that results in a condition that substantially interferes with the activities of daily living of a study patient. Disability is not intended to include experiences of relatively minor medical significance such as headache, nausea, vomiting, diarrhea, influenza, and accidental trauma (e.g., sprained ankle).
Important Medical Event Requiring Medical or Surgical Intervention to Prevent Serious Outcome:	An important medical event that may not be immediately life-threatening or result in death or hospitalization, but based on medical judgment may jeopardize the patient and may require medical or surgical intervention to prevent any of the outcomes listed above (i.e., death of patient, life threatening, hospitalization, prolongation of hospitalization, congenital anomaly, or persistent or significant

disability/incapacity). Additionally, any elective or spontaneous abortion or stillbirth is considered an important medical event. Examples of such events include allergic bronchospasm requiring intensive treatment in an emergency room or at home, blood dyscrasias or convulsions that do not result in inpatient hospitalization, or the development of drug dependency or drug abuse.

